9.4 Imputation of Missing Data

In this Phase I PK study, missing observations will be assumed to be missing completely at random (MCAR). No action will be taken to handle missing data. A participant who withdraws prior to the last planned observation in a study period will be included in the analyses up to the time of discontinuation.

10 Study Participants

The subsections in this section include specifications for reporting participant disposition and study intervention/study discontinuations. Additionally, procedures for reporting protocol deviations are provided.

10.1 Disposition of Participants and Discontinuations

The following will be presented in a summary table:

- Total number of participants screened (i.e., participants who gave informed consent)
- Number of screened participants who discontinued from the study prior to first dosing overall and grouped by the main reason for discontinuation:
 - Participant did not meet all eligibility criteria
 - Withdrew consent
 - Other (COVID-19-related and COVID-19-non-related)
- Number of treated participants
- Number and percentage of treated participants who completed study
- Number and percentage of treated participants who discontinued the study or study intervention, with the primary reason of discontinuation:
 - Adverse event
 - Lost to follow-up
 - Protocol non-compliance
 - Death
 - Withdrew consent
 - Other (COVID-19-related and COVID-19-non-related)

The number and percentage of participants will be presented by part, group of study intervention and total, where applicable. Percentages will be presented with respect to the number of treated participants, where applicable.

A listing of discontinued participants will be provided.

A listing of participants affected by the COVID-19 related study disruption by unique participant identifier will also be provided.

10.2 Protocol Deviations / Exclusion from Analysis Sets

10.2.1 Important Protocol Deviations

Listings of important protocol deviations will be provided including the date and relative day in relation to dosing in the relevant period. A distinction will be made between important protocol deviations due to COVID-19 versus not due to COVID-19. The respective important protocol deviations will be flagged accordingly.

Important protocol deviations or important events that might influence PK include, but may not be limited to the following:

- Adverse events, diarrhea etc. (these instances will be discussed on a case-by case basis)

- Vomiting after administration following oral dosing (these instances will be discussed in alignment with applicable regulatory guidelines on a case-by-case basis)
- Sample processing errors that may lead to inaccurate bioanalytical results
- Inaccurate dosing or dosing errors (e.g., dose administration delayed, dose change or missed doses)
- Pre-dose or trough sample collected after the actual dosing
- Non-compliance with food and drink requirements (e.g., non-fasted, incomplete meal consumption, caffeine intake)
- Concomitant medication, vitamins, dietary or herbal supplements

Should one or more of these events be available at the Data Review Meeting, its implication for PK evaluation will be discussed and agreed amongst relevant study team members (e.g., Sponsor Clinical Pharmacology/Biostatistics/Clinical Pharmacokinetics **C** [REDACTED] team representative). Appropriate action will be taken such as flagging individual values to be excluded from analysis.

10.2.2 Reasons Leading to the Exclusion from an Analysis Set

If participants are excluded from the PK Analysis Set, the reasons for exclusion will be listed.

Reasons for excluding individual PK concentrations will also be listed separately and flagged in the main listing.

11 Demographics and Other Baseline Characteristics

Demographics and baseline characteristics will be presented for the SAF.

11.1 Demographics

Descriptive statistics will be presented for age, height, weight, and BMI. Frequency counts and percentages will be presented for sex, race, and ethnicity. The summary will be performed overall.

BMI (kg/m^2) will be derived (i.e., not taken directly from the database) according to the following formula:

$$\text{BMI } [\text{kg}/\text{m}^2] = \frac{\text{weight } [\text{kg}]}{\text{height} [\text{cm}]^2} \times 10000$$

11.2 Medical History

Medical history will be coded using the MedDRA, most current version at time of data base lock, and listed.

The medical history will be listed by participant including PT as event category and SOC body term as Body System category.

11.3 Other Baseline Characteristics

Other baseline measurements, such as virus screen, alcohol and drugs of abuse screen, pregnancy test in women, nicotine, and alcohol consumption, will be listed.

Baseline characteristics with respect to vital signs, physical examinations, and hematology/biochemistry will be part of Section 15 (Safety Evaluation).

12 Previous or Concomitant Therapies/Procedures

Medications will be presented for the Safety Analysis Set.

Previous medications are defined as any medication discontinued prior to the administration of study intervention. Concomitant medications are defined as any medication taken during the course of the study, with a starting date greater than or equal to the administration of study intervention, or with a starting date prior to the administration of study intervention and ongoing at the time of the administration of study intervention.

The World Health Organization Drug dictionary most current version at time of database lock, will be used for coding of prior and concomitant medications and they will be described using PT as applicable.

Previous and concomitant medications will be listed. Concomitant procedures, if any, will also be listed.

13 Study Intervention: Compliance and Exposure

The dosing of each participant is monitored by the study nurse or investigator. A listing of date and time of each drug administration and each blood sampling, including time deviations as well as measured plasma concentrations, will be provided sorted by participant. Information on meal intake will be listed by participant, if provided.

14 Efficacy Analyses

Not applicable.

15 Safety Analyses

This section includes specifications for summarizing safety endpoints that are common across clinical studies such as adverse events, laboratory tests and vital signs.

All safety analyses will be performed for the Safety Analysis Set and will be presented overall by nominal timepoint, as appropriate.

Safety analyses will be done according to the as-treated principle.

15.1 Adverse Events

All AEs recorded during the study will be coded with the MedDRA, latest version at time of database lock, and assigned to a SOC and a PT.

TEAEs are those events with onset dates on or after the first administration of study intervention on Day 1. Any AE occurring before the administration of study intervention on Day 1 and resolved before administration of study intervention or not worsening after administration of study intervention on Day 1 will be included in the AE listings but will not be included in the summary tables (unless otherwise stated). These will be referred to as “pre-treatment” AEs.

In case AE-related dates are partial, the available information will be used in a conservative approach to determine whether the AE is treatment-emergent.

All analyses described in Section 15.1 will be based on TEAEs if not otherwise specified. The AE listings will include all AEs (whether treatment-emergent or not). AEs outside the on-treatment period will be flagged in the listings.

Unless otherwise specified, TEAEs will be summarized, by number and percentage of participants with the TEAE in the category of interest, as well as the number of events, in total by primary SOC and PT in alphabetical order for SOC and decreasing overall frequency for PT.

If an event was reported more than once due to change in intensity and change in relationship, the worst severity and the worst relationship to study intervention will be tabulated.

Each participant will be counted only once within each SOC or PT.

15.1.1 All Adverse Events

TEAEs and participants experiencing TEAEs will be summarized overall with:

- The number and percentage of participants with any TEAE, any related TEAE, any evobrutinib-related TEAE, any carbamazepine-related TEAE, any serious TEAE, any related serious TEAE, any evobrutinib-related serious TEAE, any carbamazepine-related serious TEAE, any severe TEAE, any related severe TEAE, any evobrutinib-related severe TEAE, any carbamazepine-related severe TEAE, any AESI, any TEAE leading to death, any related TEAE leading to death, any evobrutinib-related TEAE leading to death, any carbamazepine-related TEAE leading to death, any TEAE leading to study discontinuation
- The number and percentage of participants with at least one TEAE and the number of events by SOC and PT.
- The number and percentage of participants with TEAEs excluding SAEs and the number of events, with frequency $\geq 5\%$ in any study intervention arm by SOC and PT
- The number and percentage of participants with at least one TEAE and the number of events by severity, SOC, and PT

- The number and percentage of participants with at least one related TEAE, evobrutinib-related TEAE, carbamazepine-related TEAE and the number of events by SOC and PT
- The number and percentage of participants with at least one AESI recorded and the number of events by SOC and PT.

Unless otherwise stated, AEs will be displayed with SOC terms sorted alphabetically and PTs within each SOC term sorted in descending overall frequency.

For determining incidence counts, within each level of TEAE term, if a participant experiences more than one occurrence, the participant will only be counted once for that TEAE.

AEs related to any study intervention are those events with relationship missing, unknown or yes.

In case a participant had events with missing and non-missing severity, the maximum non-missing severity will be displayed.

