9.4.2 Safety Analyses

All safety analyses will be performed on the Safety Analysis Set.

Reference #	Endpoint	Statistical Analysis
Primary		Not applicable
Secondary		
2 - Safety	Nature, occurrence, severity, and seriousness of TEAEs	AE counts and participants with AEs will be summarized for each treatment by SOC and PT. In addition, AEs will be tabulated and listed per participant and analyzed by severity and relationship to study intervention.
	Absolute values and changes in safety laboratory tests from time of first dose to end of study participation	Safety laboratory parameters will be listed for each participant including changes from Baseline and flags for measurements outside the reference ranges, where applicable. Laboratory parameters (hematology and clinical chemistry) will be summarized by time point including both absolute values and changes from Baseline.
	Single 12-lead ECGs evaluated by Investigator from time of first dose to end of study participation	ECG data will be summarized by absolute and changes from Baseline values by treatment using descriptive statistics. Clinical noteworthy ECG findings for individual participants will be listed and summarized as appropriate.
	Vital signs assessed from time of first dose to end of study participation	Vital signs by participant, including changes from Baseline, will be listed and summarized by treatment and time point using descriptive statistics.
CCI		

AE=adverse event; ECG=electrocardiogram; PT=preferred term; SOC=system organ class; TEAE=treatment-emergent adverse event.

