8.2 Subgroup Definition and Parameterization

Not applicable.

9 General Specifications for Data Analyses

The results of this study will be reported using summary tables, figures, and data listings, as appropriate. All data will be summarized by study intervention and/or scheduled time point, as applicable.

Listings

In the individual participant data listing all individual data will be listed as measured. Repeated and unscheduled measurements will be included in the listings. All listings will be sorted by subject ID and nominal time point, if not stated otherwise.

Tables and Descriptive Statistics

All safety data will be summarized overall by nominal time point, as appropriate. All PK data will be summarized by study intervention and nominal time point. Repeated and unscheduled measurements included in the listings will not be used for statistical analyses or summaries, unless the repeated measurement was performed due to unreliable values/technical reasons, e.g., clotted samples.

Unless otherwise specified, continuous variables will be summarized using descriptive statistics, i.e. the number of participants with non-missing values (n), the number of participants with missing values (nmiss), mean, standard deviation, median, 25th percentile (Q1) and 75th percentile (Q3), minimum, and maximum. If there are no missing values the number of participants with missing values should be indicated by a 0. Mean, Median, Q1, Q3, Min, Max will have the same precision as the SDTM data (decimal places). SD will be presented with one decimal place more than the mean.

Qualitative variables will be summarized by frequency counts and percentages. Unless otherwise stated the calculation of proportions will be based on the number of participants of the analysis set of interest that received the respective study intervention for AE and PK tables and for all other evaluations the analysis set of interest [N]. Therefore, counts of missing observations will be included in the denominator and presented as a separate category.

Study day 1 for this study is defined as the start date of study intervention.

The following labels will be used for the study interventions in PK tables and listings, if not stated otherwise:

Evobrutinib: 45 mg Evobrutinib on Day 1

Carbamazepine+Evobrutinib: Carbamazepine from Day 2 to Day 25 plus 45 mg Evobrutinib on Day 19

All statistical analyses will be performed using SAS® Software version 9.2 or higher.

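### The SAP pools its TEAE tables although the protocol plans adverse events by treatment; no rule places a TEAE in a treatment period, and the change is not declared

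*SAP*

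**What the plan says.** **Protocol.** Section 9.4.2 states that "AE counts and participants with AEs will be summarized for each treatment by SOC and PT", and treats severity and relationship to study intervention as additional analyses. Section 9 of the protocol says that changes to planned analyses will be reported in the appropriate section of the analysis plan. The secondary safety objective (Section 3) concerns evobrutinib given together with carbamazepine.

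**SAP.** Section 15.1 sets the default for TEAE tables as "in total by primary SOC and PT in alphabetical order" for SOC. Section 15.1.1 introduces all six of its table bullets with "TEAEs and participants experiencing TEAEs will be summarized overall with". Section 15 says "All safety analyses will be performed for the Safety Analysis Set and will be presented overall by nominal timepoint, as appropriate". Section 9 opens permissively, "All data will be summarized by study intervention and/or scheduled time point, as applicable", but then separates the two data types: PK data go by study intervention, while "All safety data will be summarized overall by nominal time point, as appropriate".

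For percentages, SAP Section 9 uses as denominator "the number of participants of the analysis set of interest that received the respective study intervention for AE and PK tables". One bullet of 15.1.1 applies a 5% frequency filter per study intervention arm. SAP Section 7, on changes from the protocol, mentions only a possible interim data review.

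**The concern.** Each participant passes through three situations in a fixed order: evobrutinib alone, carbamazepine without a further evobrutinib dose, and evobrutinib on top of carbamazepine followed by taper. The safety objective is about the last of these. A pooled TEAE row gives the number of participants and events but not the situation in which they occurred. A participant with the same preferred term on Day 3 and on Day 20 appears as one participant and two events, with no timing.

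If the SAP is followed as written, the report will lack the by-treatment AE summary that the protocol plans, the TEAE tables will not describe the safety of the combination, and the reader will not be told that the plan changed. A programmer must also decide alone how to apply a denominator and a filter written for treatment columns to a table that has only one.

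**Working it through.** **1. Side by side.**

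| Item | Protocol 9.4.2 | SAP |
|---|---|---|
| AE counts and participants by SOC and PT | For each treatment | In total (15.1), overall (15.1.1) |
| Relationship to study intervention | In addition | Tabulated, also by drug (15.1.1) |
| Declared change | To be reported in the analysis plan (protocol Section 9) | Not listed in Section 7 |

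The permissive opening sentence of SAP Section 9 does not settle the matter, because the same section and Sections 15, 15.1 and 15.1.1 then give the specific rule for safety data. The relatedness rows do not replace the missing split: they record the investigator's causality judgement, not what the participant was receiving at onset.

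**2. Is there an assignment rule?** SAP 15.1 defines a TEAE by onset on or after the first dose on Day 1 and goes no further. For incomplete dates, "the available information will be used in a conservative approach to determine whether the AE is treatment-emergent"; this decides treatment emergence, not the period. The only treatment labels, in SAP Section 9, are stated for PK tables and listings. Borrowed for AEs, the combination label runs from carbamazepine on Day 2, so it would merge Days 2 to 18 with the combination.

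**3. Do the denominator and filter fit?** A denominator of those who received the respective intervention, and a threshold per arm, each need more than one column. The effect of the filter is nil in practice: with 18 planned participants, one participant is 1/18 = 5.6%, which already exceeds 5%. The mismatch is one of specification, not of which rows would print.

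**4. Time covered by a pooled row.** Nominal times come from the Schedule of Activities (protocol 1.3):

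- Day 1 evobrutinib dose to first carbamazepine on Day 2, after the 24-hour sample: about 1 day.
- First carbamazepine to the Day 19 evobrutinib dose: 19 − 2 = about 17 days.
- Day 19 dose to the Day 26 visit, including taper and follow-up: 26 − 19 = about 7 days.

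Total: 1 + 17 + 7 = 25 days. Shares: 1/25 = 4%, 17/25 = 68%, 7/25 = 28%. Before the Day 19 dose: (1 + 17)/25 = 72%.

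Under the two-level PK labels the split would instead be 1/25 = 4% and 24/25 = 96%. The 72% therefore depends on the partition chosen.

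**5. What can be recovered.** SAP 9.3 defines relative study day, which gives 3 for a Day 3 onset and 21 for a Day 21 onset. In a fixed calendar this places an event except on the changeover Days 2 and 19, where clock time is needed. Time since last evobrutinib dose does not do this by itself, since both onsets give about 2 days (3 − 1 and 21 − 19).

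**The case against.** The strongest reply is that little is lost. The analysis is descriptive, with no hypothesis tests. Drug-specific relatedness is tabulated, all AEs and dosing times are listed, and relative study day recovers timing. Three of the four endpoints under the safety objective (laboratory tests, ECG, vital signs) are summarised by time point, which identifies treatment in this sequence. All of this stands, and it confines the point to the TEAE summaries.

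A second reply is that neither document defines a three-period split, and that its columns would be unequal in length, small in count and confounded with time. That also stands. It limits what the split can show, but does not remove the mismatch with the protocol. The third period also mixes co-administration with taper and follow-up, so it needs to be labelled accordingly.

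Three stronger readings are tempting and are not supported:

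- A reader might infer that SAP 15.1.2 and 15.5 add to the inconsistency because they use study intervention as a grouping. The first most naturally means the drug discontinued, and the second concerns ECG interpretation. Neither conflicts with pooled TEAE tables.
- A reader might take 72% as the degree to which AE results are distorted. The documents give no event rates for this study, so no distortion of any result can be computed.
- A reader might conclude that the safety of the combination cannot be assessed. Onset information is collected and listed; what is missing is the planned summary.

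**Conclusion.** The point holds as a gap in the planned descriptive summaries. The protocol plans AEs by treatment; the SAP pools TEAEs, gives no rule for assigning them to a period, and does not declare the change. Its AE denominator and 5% filter are written for columns that the pooled tables do not have. The gap reaches the TEAE part of the secondary safety objective only. Primary PK is unaffected and no data are lost.

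As a guide to size, about 18 of 25 nominal days precede the Day 19 evobrutinib dose. That figure assumes nominal dosing times, observation to Day 26 and the three-period partition. The textual mismatch rests on no assumption.

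**What to change.** In SAP 15.1, assign each TEAE by onset date and time to one of three periods:

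1. Day 1 evobrutinib dose to before first carbamazepine.
2. First carbamazepine to before the Day 19 evobrutinib dose.
3. Day 19 evobrutinib dose to end of follow-up, stated to include taper and follow-up.

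Add a convention for missing onset times, in keeping with the conservative approach the SAP already takes to partial dates. It will matter mainly on Days 2 and 19.

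Tabulate TEAEs by period and in total. Use participants dosed in each period as denominators, count each participant once per SOC or PT within a period and once in the total, and show the period lengths (about 1, 17 and 7 days). Align Sections 9, 15, 15.1 and 15.1.1.

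If pooling is intended, declare and justify it in SAP Section 7, and correct the denominator sentence and the filter to suit a single column.

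Separately, SAP 9.3 defines time from dosing with a cocktail and sumatriptan, which this study does not give, and omits carbamazepine. Replace these with the study's own interventions.

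**Cost.** SAP wording and a few table columns; onset and dosing times are already collected. Counts per period will be small, and period is confounded with time, so the split should be presented as descriptive only.

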15.1.2 Adverse Events Leading to Discontinuation of Study Intervention

A listing of TEAEs leading to discontinuation of study intervention, or discontinuation of study, if any, will be provided.

The frequency (number and percentage) of participants with TEAEs leading to permanent discontinuation of each study intervention by study intervention will also be provided in a table.

15.2 Deaths, Other Serious Adverse Events, and Other Significant Adverse Events

15.2.1 Deaths

A listing of deaths, if any, will be provided.

15.2.2 Serious Adverse Events

A listing of SAEs, if any, will be provided.

Summary table of the number and percentage of participants with at least one SAE by SOC and PT will also be provided.

15.2.3 Other Significant Adverse Events

The following AESI were defined:

- Infections (serious, severe, and opportunistic, \geq Grade 3)
- Seizures
- Elevated lipase, elevated amylase, pancreatitis

- Liver-related events

More information can be found in the CSP, Section 8.3.7.

AESI will be identified in the AE listings. Summary table of the number and percentage of participants with at least one AESI by SOC and PT will also be provided.

